Appendix to:

[name] et al

Sentinel lymph node detection in endometrial cancer. A consolidation study.

Table 1. Participating Sites and Site-Principal Investigators

Site	Site-PI	# patients enrolled
1. Department of Obstetrics and Gynecology, Skåne University Hospital and Lund University, Lund, Sweden	[name]	XX
2. To be decided		

Supplementary appendix

[name] et al

Sentinel lymph node detection in endometrial cancer. A consolidation study.

Coordinating Center: Department of Obstetrics and Gynecology, Skåne, Lund University Hospital and Lund University, Lund Sweden.

Lead Principal Investigator: [name] MD PhD Associate Professor
Department of obstetrics and Gynecology, Division of Gynecologic Oncology
Skåne University Hospital Lund
[name]
(ph) [name]
(fax) [name]
Email: [contact]

Local Principal Investigator:

Study Coordinator: [name] MD
Department of obstetrics and Gynecology, Division of Gynecologic Oncology
Skåne University Hospital Lund
[name]
(ph)[name]
(fax) [name]
Email: [contact]

[figure not shown]
Study Statistician:

[name]. Faculty of Engineering, Lund University.

Overview study plan.

Consecutive eligible high and low risk endometrial cancer planned for robotic surgery, clinically with the primary tumor confined to the uterus (uterine stage I-II).

High risk defined as at least either of deep ($\geq 50\%$) myometrial invasion, cervical stromal invasion, endometrioid cancer FIGO grade 3, or a non-endometrioid histology. FIGO grade 1-2 endometrioid cancer with no myometrial invasion are defined as low risk.

Define/ plan also as of below:

1. **FIGO grade 1-2 endometrioid cancers regardless of myometrial invasion.**

SLN UPP and parametria. Ipsilateral reinjection only if non-display of UPP. No frozen section of SLN unless macro. Removal of nodes at typical positions for SLN (External, obturator, common) in case of non-display of UPP uni or bilaterally

2. **FIGO grade 3, undifferentiated or non-endometrioid cancers.**

SLN UPP, parametria and LPP. Ipsilateral reinjection if non-display of UPP. Removal of nodes at typical positions for SLN (External, obturator, common) in case of non-display of UPP uni or bilaterally. Full uni-bilateral presacral LND if non-display of LPP. No frozen section of SLN unless macro.

3. **Any endometrial cancer with cancer suspect pelvic or paraaortic nodes**

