In case of additional centres later including patients: The departments of pathology shall be coordinated in terms of principles for ultra sectioning and immunohistochemistry of SLN and management on non-sentinel lymph nodes.

4.0/5.0 STUDY MODALITIES/ TREATMENT

Surgical Procedures

All patients; plan for QM B2 or C1 hysterectomy stage II), adnexectomy. Omentectomy in non-endometrioid or undifferentiated cancers

Define/ plan also as of below:

1. FIGO grade 1-2 endometrioid cancers regardless of myometrial invasion.

SLN UPP and parametria. Ipsilateral reinjection only if non-display of UPP. No frozen section of SLN unless macro. Removal of nodes at typical positions for SLN (External, obturator, common) in case of non-display of UPP uni or bilaterally

2. FIGO grade 3, undifferentiated or non-endometrioid cancers.

SLN UPP, parametria and LPP. Ipsilateral reinjection if non-display of UPP. Removal of nodes at typical positions for SLN (External, obturator, common) in case of non-display of UPP uni or bilaterally. Full uni-bilateral presacral LND if non-display of LPP. No frozen section of SLN unless macro.

3. Any endometrial cancer with cancer suspect pelvic or paraaortic nodes

according to RECIST criteria (≥ 16 mm short axis). SLN detection/reinjection as for 2 above. Frozen section of SLN. Patient upfront surgery planned for pelvic and paraaortic lymphadenectomy. Pelvic and paraaortic LND if frozen section verifies cancer.

[figure not shown]
UPP- Upper paracervical pathway

LPP- Lower paracervical pathway

Parametria= upper lymphovascular paracervical tissue medial of the umbilical artery, dorsal of the supravesical artery, lateral of the medial broad ligament and ventral of the ureter.

Typical positions of SLN for definition of “SLN-anatomy”

Positions of SLN in uterine cancer following a cervical injection of ICG

Drug Information:

Indocyanine Green solution (ICG) 2.5mg/mL.

Description: ICG (Pulsion medical system, PICG0025SE, Feldkirchen Germany) is a sterile, lyophilized green powder containing 25 mg of Indocyanine green with no more than 5% sodium iodide.

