The ICG solution is prepared immediately before surgery and intended for single patient use. For preparation, 10mL of sterile water is injected directly into the lyophilized ICG in its glass vial. Invert the vial multiple times to ensure thorough mixing. Draw up 0,25 mL in six 1 mL syringes from the vial with ICG solution (2,5mg/mL) for the cervical injection. A 0.6x38mm 23Gx1 1/2 needle. The content of four of the syringes are used for the initial injection and in case of non-display of any pathway one or two of the other are used for an ipsilateral re-injection.

The ICG solution is stored at room temperature. The solution is active for 6 hours, and should be discarded after that period of time.

Manufacturer: Pulsion medical system, Feldkirchen Germany

Availability: ICG will be provided by the manufacturer to each site.

Adverse Effects if ICG: All adverse effects are allergic in nature and occur in <1% of patients. Anaphylactic or urticarial reactions have been reported in patients with or without a history of allergy to iodides. If such reactions occur, treatment with the appropriate agents (e.g. adrenalin, antihistamines, corticosteroids) should be initiated.

Contraindications: Known hypersensitivity to iodine containing compounds. Known liver failure. Radioactive iodine uptake studies should not be performed for at least 1 week following the use of ICG.

Please refer to the current ICG package insert for complete prescribing information

Injection of Indocyanine Green (ICG)

- The ICG is prepared by thorough mixing of 10mL of sterile water with the lyophilized ICG in its vial creating a 2.5mg/mL concentration. The lot number, expiration date and dose injected (mg) will be recorded.
- Six separate sterile 1mL syringes is prepared with 0.25 mL ICG solution (0.625 mg ICG) in each syringe is prepared.
- A 0.6x38 mm 23G needle is attached to each syringe for the injection. A separate back table is used for the syringes.
- The ICG injection will be performed immediately before placement of surgical port and docking the robot.
- Half the ICG volume in each syringe is injected submucosally and half the volume 3 cm into the cervical stroma at 2-4-8-and 10 O'clock respectively to a total dose of 2.5mg ICG and a total volume of 1 mL. Time for injection is recorded.
- After injection of dye, a fornix presenter without an intracervical device is placed

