- A second ipsilateral injection of 0,25mL ICG is performed in case of non-display of either of the upper (UPP) or lower (LPP) paracervical pathways after a minimum of 10 minutes observation time after ICG injection. The injection is done at 3 and 9 O'clock respectively, half the volume submucosally and half the volume 3 cm into the cervix.
- Display of the separate lymphatic pathways (UPP, LPP and IPP will be recorded after the first and if performed after the second injection).

Sentinel Node Identification

The bilateral technical success rate of SLN identification is important to determine if this technique can be transferred to clinical practice. A clear anatomically definition of what is a SLN and a strict surgical algorithm as described in this study is important. Based on recent results from our institution on cervical and endometrial cancer we expect that the bilateral pelvic SLN identification (defined as at least one SLN per hemipelvis) will be 94%. A lower than expected detection rate will not be an incentive for premature stop of accrual. Importantly, accreditation of surgeons will be performed as described and is likely important to achieve a similar success rate as in previous studies.

The sentinel nodes are defined as the juxtauterine ICG positive node with an afferent ICG positive lymphatics in each of the UPP and LPP respectively on each pelvic side with the potential of parallel lymphatics in the UPP to the external and obturator areas. These SLN are defined as **SLN type 1**.

In case of a ICG positive lymph vessel where no nodes are ICG positive in that pathway, the node where the ICG positive lymphatic channel ends is defined as **SLN type 2**.

Nodes macroscopically suspect of metastatic disease will be defined as **SLN Macro** regardless of ICG uptake but with information on ICG positivity or not.

In case of no defined SLN 1-2 macro along the UPP and no **SLN macro** (low and high risk EC) nodes at typical positions shall be removed and regarded as **SLN-anatomy** and treated as SLN by the department of pathology. Likewise all endometrial cancers of FIGO grad III, undifferentiated or of non-endometrioid histology shall have a full presacral dissection in case of non-display. Those node shall be treated as SLN by the department of pathology.

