Importantly, to secure accuracy, the positions and types of SLN will be marked on an anatomical chart, recorded on a list with anatomical locations and placed in pre-labeled jars with corresponding anatomical positions and numbers. This list is used by the department of pathology for reporting the results to minimize the risk of errors in location of nodes and which nodes are SLN's and non-SLN's. A copy of the list is kept in the patients study file.

Nodes defined as SLN will have red labels on the jars, other nodes will have black labels.

SLN's will be sent for final histological evaluation including ultrasectioning and immunohistochemistry as described. SLN's will not be sent for frozen section unless clinically motivated.

[figure not shown]
The display of ICG along the UPP shall be evaluated a minimum 10 minutes after the injection of ICG, first transperitoneally, and if not seen, after opening of the retroperitoneal avascular planes. An ipsilateral reinjection shall be performed in case of non-display of the UPP in both low risk (LREC) and high risk (HREC) endometrial cancers. A non-display of the LPP shall **not** motivate reinjection but in HREC a full presacral lymphadenectomy (LND). No presacral dissection shall be performed in LREC.

In case of non-display of the UPP despite reinjection a full lymphadenectomy in the external iliac and obturator areas shall be performed in HREC whereas in LREC LND a selective LND shall be performed including all macroscopically enlarged nodes and lymph nodes proximal in the obturator fossa and external iliac nodes in the bifurcation / between the external and internal iliac artery (typical positions of SLN's along the UPP).

To minimize disturbance by leaking ICG identification and removal of SLN's starts cranially, presacrally (along the LPP, HREC only) and continues at the pelvic side walls along the UPP. In both HREC and LREC and after removal of SLN's the upper lymphovascular parametrial tissue is removed separately (defined as the tissue along the uterine artery, medial to the obliterated umbilical artery and caudal of the supravesical artery) as it may contain lymph nodes that may not be separated from the green lymphovascular tissue and hence be the juxtauterine lymph node.

Anatomic boundaries of lymph node compartments in the female pelvis				
Lymph node compartment	Proximal limit	Lateral limit	Distal limit	Medial limit

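### The surgical algorithm contradicts itself on ICG re-injection and on dissection after UPP non-display in high-risk disease, and its HREC/LREC terms are not tied to the surgical groups

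*Combined protocol and SAP*

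**What the plan says.** The rules stand in the Overview study plan and in section 4.0/5.0.

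**Re-injection.** The ICG injection section states: "A second ipsilateral injection of 0,25mL ICG is performed in case of non-display of either of the upper (UPP) or lower (LPP) paracervical pathways". Drug Information agrees: "in case of non-display of any pathway one or two of the other are used for an ipsilateral re-injection". For group 1 (grade 1-2 endometrioid), the Overview and Surgical Procedures say "Ipsilateral reinjection only if non-display of UPP". For group 2 (grade 3, undifferentiated or non-endometrioid) they name UPP non-display and are silent on the LPP. Sentinel Node Identification says that LPP non-display shall not "motivate reinjection but in HREC a full presacral lymphadenectomy (LND".

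**Extent after UPP non-display.** Groups 1 and 2 carry the same sentence: "Removal of nodes at typical positions for SLN (External, obturator, common) in case of non-display of UPP uni or bilaterally". The SLN-anatomy rule in Sentinel Node Identification covers both risk classes: "low and high risk EC) nodes at typical positions shall be removed and regarded as" SLN-anatomy. Later in that section comes: "In case of non-display of the UPP despite reinjection a full lymphadenectomy in the external iliac and obturator areas shall be performed in HREC". There, typical positions belong to a selective dissection kept for LREC.

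**LPP mapping and presacral dissection.** The later paragraphs of Sentinel Node Identification assign these by HREC/LREC. The surgical groups and the SLN-anatomy paragraph assign them by grade and histology. The Overview defines high risk as any one of deep (at least 50%) "myometrial invasion, cervical stromal invasion, endometrioid cancer FIGO grade 3, or a non-endometrioid histology", and low risk as grade 1-2 endometrioid cancer without myometrial invasion. Group 1 takes grade 1-2 endometrioid tumours at any invasion depth.

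The Overview also lists a complete pelvic lymphadenectomy with no condition attached.

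**The concern.** The algorithm is the intervention under test. Section 1 evaluates an anatomically based algorithm, and Sentinel Node Identification says a strict one is important. Two surgeons who each follow the protocol could treat the same patient differently.

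This reaches the endpoints in three ways:

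- Pathology treats SLN-anatomy nodes as SLNs, and section 8.0 counts them in the detection rate. Other nodes get routine sectioning only. The extent rule can therefore change which nodes are removed, ultrastaged and counted.
- Section 8.0 includes re-injection in the recorded intervention time, and section 1 makes procedure time an objective.
- Section 1 also makes ICG complications an objective, and the re-injection rule changes ICG exposure.

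Adherence to the protocol, which section 3 asks site visits to ensure, cannot be judged where the protocol gives two answers.

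**Working it through.** **1. Re-injection when only the LPP fails to display**

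| Place | Re-inject? |
|---|---|
| Drug Information | Yes |
| Injection of ICG | Yes |
| Surgical Procedures, group 1 | No |
| Surgical Procedures, group 2 | Silent on LPP |
| Sentinel Node Identification | No |

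Inputs from Drug Information and the injection section: 2.5 mg/mL, 0.25 mL per syringe, four syringes at first injection, six prepared, 0.25 mL per re-injected side.

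- First injection: 4 × 0.25 mL = 1 mL; 1 mL × 2.5 mg/mL = 2.5 mg. This reproduces the protocol's stated volume and dose.
- Each re-injected side: 0.25 mL × 2.5 mg/mL = 0.625 mg.
- One side: 2.5 + 0.625 = 3.125 mg (0.625/2.5 = 25% more).
- Both sides: 2.5 + 2 × 0.625 = 3.75 mg (1.25/2.5 = 50% more).
- Prepared maximum: 6 × 0.625 = 3.75 mg.

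So the total is 2.5 mg under Sentinel Node Identification and 3.125 or 3.75 mg under the other two sections. Bilateral UPP non-display reaches 3.75 mg under every reading, so the conflict creates no new dose ceiling.

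**2. Extent after UPP non-display in high-risk disease**

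- Group 2 and the SLN-anatomy rule: nodes at typical positions, which the groups list as external, obturator and common.
- Later in Sentinel Node Identification: full external iliac and obturator lymphadenectomy for HREC, contrasted with typical positions for LREC.

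Reading HREC as group 2 does not remove this conflict, because group 2 itself carries the typical-positions rule and the SLN-anatomy rule names high-risk disease. The rules overlap in the external and obturator areas. They differ in extent beyond the typical positions, and in the common iliac station, which the HREC rule does not name and the table of anatomic boundaries treats as a separate compartment.

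**3. LPP mapping and presacral dissection**

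Take a grade 1-2 endometrioid tumour with deep invasion. The surgical groups place it in group 1: UPP and parametria only. The Overview definition makes it high risk, and under the HREC rules it then gets LPP mapping, with presacral dissection if the LPP is not displayed. The two agree only if HREC/LREC means groups 2/1, which no section states.

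Grade 1-2 tumours with invasion above 0 but below 50% and no cervical stromal invasion meet neither Overview definition.

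**4. Patients affected**

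This needs display rates for each pathway. The only related figure, 94%, is expected bilateral detection of at least one SLN per hemipelvis. It does not separate UPP from LPP, so no count can be derived.

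**The case against.** The strongest reply concerns the third part. The groups are introduced as a way to define as well as plan, and the SLN-anatomy paragraph gives presacral dissection to exactly the group 2 tumours. If HREC/LREC is shorthand for groups 2/1, the sections agree on LPP mapping and presacral dissection. A reader might infer a flat contradiction here, but the documents support only an ambiguity: the shorthand is plausible, yet unstated and at odds with the Overview's definition, the only one given.

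On extent, a full external iliac and obturator lymphadenectomy also removes the typical-position nodes in those areas. A surgeon following the HREC rule therefore departs from the group 2 rule only at the common iliac station. That stands, but the reverse does not: the typical-positions rule does not satisfy the HREC rule.

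Re-injection and dose are recorded for each patient, so practice can be audited. That helps with patients already treated but does not tell a surgeon what to do next.

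A reader might also infer that the 50/50 assumption in section 11 can no longer be checked. That goes too far: section 1 relies on final myometrial invasion, cervical invasion, type and grade, so most patients can be classified afterwards. What is missing is a class for the intermediate group.

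**Conclusion.** The rules are wrong as written. This is an internal inconsistency, not a design choice. The re-injection conflict is direct. The extent conflict in high-risk disease is real, though the rules partly overlap. The third part is an undefined link between two classification schemes plus a gap in the risk definition.

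The one computable size is ICG exposure in a patient with LPP-only non-display: 2.5 mg against 3.125 or 3.75 mg, assuming the stated volumes are followed and each affected side is re-injected once.

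A reader might infer that the primary test is invalid or biased. The documents do not support this. The 8% against 12% comparison, the 362 patients and the interim limits use none of these rules, and the effect on the positive rate cannot be estimated. The case for correction is that surgeons receive opposite operative and drug-administration instructions within the intervention being evaluated.

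**What to change.** - Reconcile the Overview study plan, Surgical Procedures, Drug Information, Injection of ICG and Sentinel Node Identification so that three rules each appear in one form only: the re-injection trigger, the extent after UPP non-display, and who gets LPP mapping and presacral dissection. The sponsor's clinicians must choose the content. Align the Overview's unconditional pelvic lymphadenectomy with the result.
- Make the HREC/LREC definition exhaustive and state whether it equals surgical groups 2/1. For analysis, assign the class from final histology, as section 1 implies, so that the observed mix can be reported against the 50/50 assumption.
- For patients already operated on, use the recorded ICG dose and the re-injection and display grid to identify which re-injection rule was applied. The informative cases are sides where the UPP displayed and the LPP did not after the first injection. The list of nodal specimens shows which stations were sampled, but may not separate full from selective dissection.

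The cost is protocol wording, a note to surgeons and a record check for patients operated on since January 2019. Whether any procedure is added depends on the rule the sponsor chooses. Handling of patients already treated can be described but not harmonised.

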5.0 TREATMENT PLAN/ FOLLOW UP

Patients with metastatic SLN's shall be planned for a restaging procedure including pelvic and paraaortic lymph nodes.

Importantly, all intraoperative adverse events associated with the study intervention and the study drug (ICG) will be recorded in protocol as the separate time used for the detection and removal on SLN's. Likewise, complications associated with the restaging procedure shall be included on an intention to treat basis.(additional CRF)

All adverse events, including postoperative until 30 days, shall be evaluated whether attributable to the study intervention or not.

Measurement of leg volume as an objective parameter of lymphedema shall be performed at one and two year follow up and at symptoms.

Symptoms associated with lymphedema shall be evaluated by a designated QoL Form used before surgery, after surgery at symptoms, and at one and two years after surgery. A symptoms score shall be used at every follow up.

NOTE: Surgeons' skill and adherence to protocol will be verified as described above.

6.0 TREATMENT MODIFICATIONS

In case of conversion to open surgery before identification and removal of SLN's the patients should be included in evaluation of adverse events and feasibility on an intention to treat basis but not included in the calculation of sensitivity and negative predictive values for the sentinel node concept.

A pelvic lymphadenectomy shall be performed based on definition of "SLNmacro" and/or "SLN-anatomy". SLN macro shall be evaluated with frozen section and if positive a paraaortic lymphadenectomy shall be performed unless contraindicated.

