Appendix 1. Basic data

Sentinel node EC consolidation study

Studie Sentinel node med ICG vid Endometriecancer Patientuppgifter Sida 1/2

Date:..... Personal identification number:.....

CRF number (by study coordinator)

Endometrial cancer:

Histological type/ FIGO grade: DNA-analyses: diploid / non-diploid

Tumor size US/MR Length_____ Anteriopost _____ width_____ mm

Myometrial invasion >50% enligt MR / ultraljud: yes no

Uterine serosal involvement/ locally advanced tumor yes no

Cervical stromal invasion MR /US/preop hist: yes no

Enlarged pelvic nodes / RECIST >=16mm short axis yes* no

Enlarged paraaortic nodes / RECIST>=16mm short axis yes* no

Locally advanced cancer/distant metastases yes** no

Comorbidity: Overall WHO performance grade:

 None	 Hypertension	 Heart disease
 Diabetes mellitus	 COL	 Thromboembolic
 Ongoing anticoag treatm	 Neurologic disorder	 Other specify

Studie Sentinel node med ICG vid Endometriecancer
Patientuppgifter
Sida 2/2

Previous intrabdominal surgery

- no
- Upper/ lower midline incision
- Pfannenstiel incision.....
- Laparoskopy/ robot:.....
- Other, specify.....

Parity / vaginal deliveries

Heredity cancer: no/ yes: specify.....

Length meter Weight

* Plan for frozen section of SLN and SLN macro and full staging. See inclusion criteria file.

**Exclude from study

WHO Performance status

Grade	Explanation of activity
0	Fully active, able to carry on all pre-disease performance without restriction
1	Restricted in physically strenuous activity but ambulatory and able to carry out work of a light or sedentary nature, e.g., light house work, office work
2	Ambulatory and capable of all selfcare but unable to carry out any work activities. Up and about more than 50% of waking hours
3	Capable of only limited selfcare, confined to bed or chair more than 50% of waking hours
4	Completely disabled. Cannot carry on any selfcare. Totally confined to bed or chair
5	Dead

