Appendix 2 Surgical protocol

Date

Surgeon.....Assisting surgeon.....

OR nurse.....Circulating nurse.....

Included as/ planned surgery

- Low risk endometrial cancer. SLN only
- High risk endometrial cancer, SLN only
- High/ low risk endometrial cancer SLN+ pelvic+ paraaortic LND due to preop/ intraop suspect nodes

Reason for an intraoperative deviation from a planned surgery

Previous surgery

- 1 No
- 2 App
- 3 Pfannenstiel
- 4 Midline upper
- 5 Midline lower
- 6 Laparoscopy/ robot
- 7 other, specify

Vikt (kg)

Längd (m)

Surgery **(specify all)**

- 1 Radical hysterectomy+adnex , QM type
- 2 Enkel hysterektomi+ adnex
- 3 Sentinel node UPP +LPP
- 4 Sentinel node UPP only
- 5 Full pelvic LND
- 6 Paraaortic LND to LRV
- 7 Paraaortic LND to IMA
- 8 Omentectomy
- Other specify

Pat in OR	time.
First Dr's procedure	time
Time for SLN Onset dissection incl reinj	Minutes:
Last stitch	time
Pat out OR	time

Uterus weight (g)

**Insufflation
technique** Palmer point direct entry
 Hasson
 Verress needle

**Adhesiolysis before
onset of surgery** no
 Yes

Total Time for adhesiolysis (before and after docking) (minutes).....

Nr robot instruments 2
 3
 4
 5
 6

Assistant trocar 1 12mm disp non-disp
 2 15 mm disp non-disp
 3 18 mm disp non-disp
 4 5 mm disp non-disp

**Additonal
instruments** Endobag,nr_____
 Tachyseal,/ floseal, nr_____
 Other specify_____

Bleeding ml_____

Transfusion No
 Yes nr units:_____

,

Conversion no
 Yes to laparotomy

Cause of conversion Robot, technical problem;; specify: _____

Surgery, specify: _____

Anesthesiologically cause; specify: _____

Complications during insufflation or adhesiolysis None
 Yes. Specify: _____

Complications during SLN removal No
 Yes. Specify: _____

Complications during remaining pelvic LND No Not performed
 Yes. Specify: _____

Complications during remaining paraaortic LND No Not performed
 Yes. Specify: _____

Complications during hysterectomy No Not performed
 Yes. Specify: _____

Technique for removal of uterus vaginally without bag vaginally with Endobag
 Through abdominal wall in bag, specify why and where.

Technique for removal of nodes Through assistant port in bag/container
 vaginally in bag

Nodal tissue divided in abdomen to an No yes specify

**enable removal
through port?**

Closure of fascia

- Assistant port
- Optics port (SI robot)
- Other ports, specify: _____

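### Section 6 refers to sensitivity and NPV, but if the treatment sections govern, most SLN-negative women have no reference dissection and the overall algorithm's sensitivity tends towards 100% whatever its true value

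*Combined protocol and SAP*

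**What the plan says.** **The measure.** Section 6.0 (Treatment modifications) keeps patients converted to open surgery before SLN removal in the safety and feasibility evaluation, but they are "not included in the calculation of sensitivity and negative predictive values for the sentinel node concept". No formula, reference standard or denominator is given there or elsewhere. Section 1 (Objectives) and Section 11 compare the observed SLN-positive percentage with an expected proportion. Section 8 evaluates a detection rate, for all SLN types together and for ICG-defined SLN (types 1-2) separately.

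**Who is dissected beyond the SLN.**
- Sections 4.0/5.0, groups 1 and 2: further nodes are removed only where a pathway is not displayed. Under Sentinel Node Identification, nodes taken from typical positions count as SLN-anatomy. Of the presacral dissection for non-display it says: "Those node shall be treated as SLN by the department of pathology".
- Group 3 (suspect nodes): "Pelvic and paraaortic LND if frozen section verifies cancer". Appendix 1 says of the same women: "Plan for frozen section of SLN and SLN macro and full staging".
- Section 5.0 (Treatment plan/follow up): patients with metastatic SLN "shall be planned for a restaging procedure including pelvic and paraaortic lymph nodes".
- Appendix 2 offers a low-risk SLN-only category, "High risk endometrial cancer, SLN only", and "High/ low risk endometrial cancer SLN+ pelvic+ paraaortic LND due to preop/ intraop suspect nodes".
- Section 11 presents SLN as replacing full lymphadenectomy in high-risk disease. Its lymphedema comparison sets 88% SLN-negative women against 12% SLN-positive women who are restaged.
- Section 6.0, second paragraph: a pelvic lymphadenectomy is based on SLN-macro and/or SLN-anatomy, and only the paraaortic part depends on frozen section. It is unclear whether this applies only after conversion.
- The Overview study plan lists a full pelvic lymphadenectomy with no condition attached.

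**The concern.** Sensitivity needs a count of false negatives: women with pelvic nodal metastases whose SLN are negative. Such a woman is found only if nodes outside the index procedure are removed and examined. Under the treatment sections that mainly happens after a positive SLN or a positive frozen section. Verification then depends on the result of the test being verified.

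A sensitivity calculated over all evaluable patients would mostly reflect how few SLN-negative women were dissected. Section 2 quotes 98% sensitivity from the centre's own data. The new figure would probably appear to match or exceed it even if the true value were lower. Section 10 plans continuous monitoring of potential false negatives but names no way of finding them.

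**Working it through.** **1. The plan's own figure.** Inputs from Section 11: null 8%, alternative 12%, one-sided alpha 5%, power 80%, interim at 150 patients, futility at 12 or fewer, rejection at 22 or more. An exact two-stage binomial search gives a smallest total of 362, with final rejection at 38 or more (computed; the plan does not state this boundary). Alpha is 0.0497 and power 0.8015, so 362 reproduces. Sensitivity does not enter this calculation.

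**2. Inputs for the illustration.**
- N = 362 and prevalence 12% (Section 11).
- True sensitivity Se: 98% (Section 2); 90% and 95% are assumptions.
- f, the fraction of SLN-negative women with a reference dissection: not in the documents. Shown at 0%, 10%, 25% and 100%, with dissection assumed independent of nodal status.

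**3. Apparent sensitivity.** Diseased D = 0.12 × 362 = 43.44; non-diseased = 318.56. TP = D × Se, FN = D − TP, apparent Se = TP / (TP + f × FN).

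At Se = 90%: TP = 39.10, FN = 4.34, SLN-negative = 362 − 39.10 = 322.9. At f = 10%: 39.10 / (39.10 + 0.434) = 98.9%.

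| True Se | Missed women | f = 0% | 10% | 25% | 100% |
|---|---|---|---|---|---|
| 90% (assumed) | 4.34 | 100% | 98.9% | 97.3% | 90.0% |
| 95% (assumed) | 2.17 | 100% | 99.5% | 98.7% | 95.0% |
| 98% (Section 2) | 0.87 | 100% | 99.8% | 99.5% | 98.0% |

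**4. Chance of seeing no false negative**, with 43 diseased women: (1 − (1 − Se) × f)^43.
- Se = 90%: 100%, 65%, 34% and 1% at f = 0%, 10%, 25% and 100%.
- Se = 98%: 0.98^43 = 42% even with full dissection.

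**5. Confidence interval when no miss is seen.** The exact 95% lower limit for n/n is 0.025^(1/n). For 39/39 it is 91.0%, which excludes an assumed true 90%. For 41/41 it is 91.4% and for 42/42 it is 91.6%, so true values of 95% and 98% are not excluded.

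**6. NPV at Se = 90%.** True NPV = 318.56 / 322.9 = 98.65%.
- Undissected women counted as negative: 1 − f × FN / 322.9 = 100%, 99.9% and 99.7% at f = 0%, 10% and 25%. Inflation is at most 1.35 points.
- Verified subset only: 98.65% under random dissection. If 15% of missed and 5% of truly negative women are dissected, 15.93 / (15.93 + 0.65) = 96.1%. With those rates reversed, 47.78 / (47.78 + 0.22) = 99.5%. The direction depends on who is dissected.

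**7. Full dissection** would remove the bias but not the imprecision: 39/43 has an exact 95% interval of 77.9-97.4%, and 42/43 has 87.7-99.9%.

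**The case against.** The strongest objection is that Section 6 sets a conversion rule, not an analysis. It says who is left out of a calculation and fixes no denominator, so a verified-subset analysis fits the same words. That stands, and it is why the point concerns an undefined measure that invites a biased calculation. But no other text fixes the population for sensitivity or NPV, so an unqualified accuracy figure could be reported under it.

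The overview's unconditional lymphadenectomy, if it governs, supplies the reference dissection and removes the bias. This also stands. The sections on treatment, restaging and statistics and the surgical form point the other way, but only the sponsor can settle it.

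Section 6's second paragraph and the staging note in Appendix 1 may give some SLN-negative women a dissection. Those women would have suspect nodes, non-display or a conversion, and are unlikely to be most of the SLN-negative group.

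Stronger readings that a reader might infer, and that the documents do not support:
- *Non-mapped women give a verified fraction.* The plan expects that "bilateral pelvic SLN identification (defined as at least one SLN per hemipelvis) will be 94" per cent, which suggests 6% verified. But nodes removed for non-display are handled as SLN and cannot reveal a miss by the overall algorithm.
- *No observed false negative is the expected result, with an interval that excludes the truth.* At an assumed 90% the chance is 65% at 10% dissected but only 34% at 25%. The interval excludes the truth at 90%, not at 95% or the documented 98%.
- *The separate type 1-2 evaluation fails too.* SLN-macro and SLN-anatomy nodes can show misses there, although they do not verify women who mapped and were negative.
- *Recurrence fills the gap.* Appendix 3 records its site, but the plan does not name it as a reference standard.

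**Conclusion.** The point holds conditionally. If the treatment sections govern, sensitivity of the overall SLN algorithm, taken over all evaluable patients, tends towards 100% whatever its true value. At an assumed 90% the inflation is 10, 8.9 or 7.3 points with 0%, 10% or 25% of SLN-negative women dissected. At the documented 98% it is at most 2 points. NPV inflation is at most 1.35 points at 90%, and only if undissected women are counted as true negatives.

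These sizes rest on 12% prevalence in 362 patients, random dissection and a dissected fraction that the documents do not give. A reader might infer that the primary result is compromised. It is not: the 12% versus 8% test and the 362 do not use sensitivity. What is at stake is whether the trial can make an accuracy claim. Because the plan contradicts itself on who is dissected, confidence that the bias would arise is moderate.

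**What to change.** 1. The sponsor reconciles the Overview study plan, Sections 4.0/5.0, the follow-up section, Section 6.0, Section 11 and Appendices 1 and 2 on who undergoes lymphadenectomy, and states which text applies. That choice is not for this review.
2. Unless all patients have a reference dissection, replace the two accuracy measures in Section 6 with the detection rate that Section 8 already uses. Alternatively, report sensitivity and NPV only in a pre-defined subset with a reference dissection. State how many SLN-negative women it contains and why they were dissected. Label the result as partially verified, with sensitivity likely biased upward where dissection depends on SLN positivity and the direction of NPV bias depending on selection.
3. Report the false negatives monitored under Section 10 together with the number of SLN-negative women dissected.

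**Cost.** Beyond the reconciliation in step 1, one clause in Section 6 and one added count in the monitoring. The primary test, sample size and data collection do not change. The downside is that no unqualified sensitivity or NPV claim can be made, and a verified-subset estimate would be small and selected.
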